5. MILESTONES

The initial planned dates for key milestones in this study are outlined below.

Milestone:	Planned Date:
Start of data collection ^a	Q1 2022
Monitoring report	Q3 2022
Data extraction (querying) for final study report ^b	Q2-Q3 2023
End of data collection ^c	Q1 2025
Final report to FDA	Q3 2025

^a Start of data collection is the planned date for starting data extraction for the monitoring phase.

b Data sources have a 6-12 month lag for data incorporation; thus, data extraction (querying) Q2-Q3 2023 will include data through ~ Q2-Q3 2022.

^c End of data collection is the planned date that the analytical dataset (the minimum set of data required to perform the statistical analyses for the primary objective) is completely available. This includes time to conduct analyses following chart validation.

LIST OF ABBREVIATIONS AND DEFINITIONS OF TERMS

Abbreviations

ADEM Acute disseminated encephalomyelitis
AESI Adverse event of special interest
ATC Anatomical Therapeutic Chemical
BLA Biologic License Application
CDC Center for Disease Control
CHI Comprehensive Health Insights

CI Confidence interval

CMA Conditional marketing authorization

CNS Central nervous system

COPD Chronic obstructive pulmonary disease

DRB Designated Regulatory Body

EDMS electronic document management system

EEA European Economic Area
EMA European Medicines Agency
EUA emergency use authorization
FDA Food and Drug Administration

FISMA Federal Information Security Management Act HIPAA Health Insurance Portability and Accountability Act

HPHCI Harvard Pilgrim Health Care Institute

HPV Human papilloma virus

ICH International Conference on Harmonization

IEC Independent Ethics Committee
IRB Institutional Review Board
mRNA Messenger ribonucleic acid

MedDRA Medical Dictionary for Regulatory Activities

NAAT Nucleic acid amplification test

NIST National Institute of Standards and Technology

NNH Number needed to harm
PASS Post-authorization safety study
PPV Positive predictive value

PRISM Post-licensure rapid immunization safety monitoring

PRO patient-reported outcome(s)

QA Quality assurance RNA Ribonucleic acid S spike protein

SAP Statistical Analysis Plan

SARS Severe acute respiratory syndrome

SARS-CoV-2 severe acute respiratory syndrome coronavirus(-2)

SAS Statistical Analysis System
SCDM Sentinel Common Data Model
SCRI Self-Controlled Risk Interval

SES socioeconomic status

SPEAC Safety Platform for Emergency vACcines

UK United Kingdom US United States

VRBPAC Vaccines and Related Biologics Products Advisory Committee

WHO World health organization

Definition of Term(s)

Acute event event event event do occur within 60 days of vaccination

Non-acute event event events expected to occur > 60 days after vaccination

Registry An organized system that uses observational study methods to collect uniform data (clinical

and other) to evaluate specified outcomes for a population defined by a particular disease, condition, or exposure, and that serves 1 or more predetermined scientific, clinical, or

policy purposes

Study The term "study" indicates the collection of data for research purposes only. The use of this

term in no way implies that any interventional treatments or procedures, planned or

otherwise, have been provided or performed.

Retrospective A study that has all information collected from source data or a retrospective database.

Normally, there is no new collection of information from the individual, although this is

Normally, there is no new collection of information from the individual, although this may be required to address specific questions. Studies/Programs/Related Research Activities with only 1 visit can be considered prospective or retrospective bearing in mind this

definition and the source of information

Post-Authorization Any study relating to an authorized medicinal product conducted with the aim of

Safety Study (PASS) identifying, characterizing, or quantifying a safety hazard, confirming the safety profile of the medicinal product, or of measuring the effectiveness of risk management measures

Washout period The disease-specific period of time required prior to COVID-19 vaccination will be defined

to more plausibly identify incident cases

Buffer period The period of time required between risk and control periods to minimize the residual risk

attributable to the vaccine

Algorithm A procedure for solving a mathematical problem (finding the greatest common divisor) in a

finite number of steps that frequently involves repetition of an operation. A medical algorithm includes decision tree approaches to healthcare treatment, medical diagnosis, or

medical prescription

Primary series A complete initial COVID-19 vaccination defined as 2 mRNA vaccine doses or at least 1

dose of Ad26.COV2.S vaccine within labeling guidelines

6. BACKGROUND AND RATIONALE

6.1. Background

SARS-CoV-2 Virology and COVID-19 Disease Burden

The severe acute respiratory syndrome coronavirus-2 (SARS-CoV-2) is an enveloped, positive-sense, single-stranded ribonucleic acid (RNA) Beta coronavirus (Coronaviridae Study Group of the International Committee on Taxonomy of Viruses 2020, Wu 2020). It was first identified following reports of a cluster of acute respiratory illness cases in Wuhan, Hubei Province, China in December 2019 (Li Q 2020). Early epidemiological investigations suggested that the majority of early cases were linked to a food market, with patients infected through zoonotic or environmental exposure, followed by the subsequent spread of infection by human-to-human transmission among close contacts (Li Q 2020). However, there is some controversy about the initial origin of the virus (Cyranoski 2020). Genomic sequencing was performed on bronchoalveolar lavage fluid samples collected from patients with viral pneumonia admitted to hospitals in Wuhan, which identified a novel RNA virus from the family Coronaviridae (Lu 2020, Wu 2020). Phylogenetic analysis of the complete viral genome revealed that the virus, SARS-CoV-2, is part of the subgenus Sarbecovirus of the genus Betacoronavirus, and is most closely related (approximately 88% identity) to a group of severe acute respiratory syndrome (SARS)-like coronaviruses previously sampled from bats in China (Lu 2020).

As of 21 December 2021, 275,614,347 cases and 5,364,386 deaths from COVID-19 have been reported worldwide. In the US, approximately 51,102,357 cases and 807,974 deaths have been reported (Johns Hopkins CSSE 2021).

Ad26.COV2.S Vaccine

Ad26.COV2.S (also known as Ad26COVS1, VAC31518, JNJ-78436735) is a monovalent vaccine composed of a recombinant, replication-incompetent adenovirus type 26 (Ad26) vector, constructed to encode the SARS-CoV-2 Spike (S) protein, stabilized in its prefusion conformation.

The S protein is the major surface protein of coronaviruses. Different animal models have been used for the evaluation of candidate vaccines against SARS-CoV, and the common conclusion that has emerged is that the viral S protein is the only significant target for neutralizing antibodies (Buchholz 2004, Sui 2005, Zhang 2004, Zhou 2004) and the only viral protein that can elicit protective immunity in animal models (Berry 2004, Bisht 2004, Bukreyev 2004, Subbarao 2004, Yang 2004).

Ad26.COV2.S encodes a membrane-bound full-length S protein derived from a SARS-CoV-2 clinical isolate (Wuhan, 2019, whole genome sequence NC_045512), with 2 amino acid changes in the S1/S2 junction that knock out the furin cleavage site, and 2 proline substitutions in the hinge region.

Safety concerns have been identified from post-authorization safety surveillance data in Vaccine Adverse Events Reporting System (VAERS), which include thrombosis with thrombocytopenia syndrome (TTS) and Guillain-Barré syndrome and have been added to the Fact Sheets. Potential

emerging safety concerns currently under evaluation include thromboembolic events (TEEs), myocarditis and pericarditis, and immune thrombocytopenia (ITP). (FDA Briefing Document 2021)

6.2. Overall Rationale for the Study

On 27 February 2021, the United States (US) Food and Drug Administration (FDA)on recommendation by the Vaccines and Related Biological Products Advisory Committee (VRBPAC), granted Emergency Use Authorization (EUA) for the Ad26.COV2.S vaccine for use in individuals 18 years of age and older based on the totality of scientific evidence available demonstrating that the benefits of the vaccine outweigh the risks (US FDA 2021). On 20 October 2021, the FDA authorized the use of a single booster dose of Janssen COVID-19 Vaccine as a homologous booster at least 2 months after completion of the primary vaccination, and as a heterologous booster following completion of a primary vaccination with another authorized or approved COVID-19 vaccine. On 19 November 2021, the FDA formally amended the EUA for Janssen COVID-19 Vaccine to authorize the vaccine as a single booster dose following completion of primary vaccination with another authorized or approved COVID-19 vaccine (ie, as a heterologous booster dose) in individuals aged 18 years of age and older. The dosing interval for the heterologous booster dose is the same as that authorized for a booster dose of the vaccine used for primary vaccination. In addition, the Fact Sheet for Healthcare Providers Administering Vaccine (Vaccination Providers) was updated to state that data support the effectiveness of a booster dose when administered at an interval of longer than 2 months after primary vaccination with the Janssen COVID-19 Vaccine. (US FDA 2021) On 14 December 2021 based on reports to the Vaccine Adverse Events Reporting System (VAERS), a passive surveillance system, the FDA revised the EUA Fact Sheet based on evidence for an increased risk of TTS with onset of symptoms approximately 1 to 2 weeks after administration of the Janssen COVID-19 Vaccine. On 05 May 2022, the FDA further revised the EUA, limiting use of the Ad26.COV2.S vaccine "to individuals 18 years of age and older for whom other authorized or approved COVID-19 vaccines are not accessible or clinically appropriate, and to individuals 18 years of age and older who elect to receive the Janssen COVID-19 Vaccine because they would otherwise not receive a COVID-19 vaccine" (US FDA 2022).

On 11 March 2021, The European Medicines Agency (EMA) Committee for Medicinal Products for Human Use (CHMP) recommended conditional marketing authorization for the Ad26.COV2.S vaccine. On 22 April 2021, a new warning on thrombocytopenia and coagulation disorder was added and the adverse drug reaction (ADR) thrombosis in combination with thrombocytopenia was added. On 9 July 2021, a contraindication was added for individuals with a history of Capillary Leak Syndrome (CLS). On 23 July 2021, Guillain-Barré Syndrome was added as an ADR with frequency of rare. On 3 September 2021, diarrhoea and paraesthesia as ADRs with uncommon frequency and hypoesthesia, lymphadenopathy, vomiting, and tinnitus as ADRs with rare frequency. On 1 October 2021, the EMA requested to add a new warning on immune thrombocytopenia (ITP), and to add dizziness and ITP to the list of ADR with frequencies of uncommon and not known, respectively. On 11 October 2021, the EMA revised the labeling to include venous thromboembolism as an ADR. On 16 December 2021, the EMA authorized a booster dose (second dose) of 0.5 mL of COVID-19 Vaccine, which may be administered

intramuscularly at least 2 months after the primary vaccination in individuals aged 18 years and older. Additionally, a booster dose of the COVID-19 Vaccine Janssen (0.5 mL) may be administered as a heterologous booster dose following completion of primary vaccination with another approved COVID-19 vaccine in the EU.

This protocol outlines a Post-Authorization Safety Study (PASS) as a retrospective, observational, propensity-scored matched cohort study utilizing health insurance claims and electronic health records to assess the risk of prespecified adverse events of special interest (AESIs) following vaccination with Ad26.COV2.S.

7. RESEARCH QUESTION AND OBJECTIVES

This study aims to assess the risk of developing prespecified AESIs following administration of Ad26.COV2.S.

Objectives

• The primary objective for this study is to assess, in adults aged 18 years and older, the potential association between the occurrence of predefined AESIs and vaccination with Ad26.COV2.S within disease-specific risk periods in individuals exposed to the first dose of Ad26.COV2.S vaccine, as compared with either 1) individuals exposed to the first dose of BNT162b2 vaccine for non-acute events or 2) for acute events during a control window within the same individual

Endpoints

The primary analysis endpoints for this study are to estimate:

- the incidence of anaphylaxis **within 0-2 days** in individuals vaccinated with the Ad26.COV2.S vaccine and in corresponding individuals vaccinated with the BNT162b2 vaccine, or during a control window within the same individual
- the incidence of generalized convulsion, arrhythmia, acute kidney failure or acute hepatic failure within 1-14 days in individuals vaccinated with the Ad26.COV2.S vaccine and in corresponding individuals vaccinated with the BNT162b2 vaccine, or during a control window within the same individual
- the incidence of cardiac inflammatory disorders (including myocarditis and pericarditis) or sensorineural hearing loss within 1-21 days in individuals vaccinated with the Ad26.COV2.S vaccine and in corresponding individuals vaccinated with the BNT162b2 vaccine or during a control window within the same individual
- the incidence of
 - thromboembolic events: microangiopathy, disseminated intravascular coagulation, deep vein thrombosis (DVT), pulmonary embolism (PE), cerebral vein thrombosis, peripheral thrombosis, hemorrhagic and non-hemorrhagic strokes, acute myocardial infarction, coronary artery disease (including acute myocardial infarction), thrombosis with thrombocytopenia within 1-28 days in individuals vaccinated with the Ad26.COV2.S vaccine and in corresponding individuals vaccinated with the BNT162b2 vaccine or during a control window within the same individual

- heart failure, and stress cardiomyopathy within 1-28 days in individuals vaccinated with the Ad26.COV2.S vaccine and in corresponding individuals vaccinated with the BNT162b2 vaccine or during a control window within the same individual
- composite endpoints within 1-28 days in individuals vaccinated with the Ad26.COV2.S vaccine and in corresponding individuals vaccinated with the BNT162b2 vaccine or during a control window within the same individual
 - o venous thrombosis, including PE and DVT
 - o arterial thrombosis, including coronary artery disease and non-hemorrhagic stroke
 - o stroke, including non-hemorrhagic and hemorrhagic strokes
- the incidence of encephalitis (including acute demyelinating encephalomyelopathy and meningoencephalitis), Guillain Barré Syndrome, Bell's palsy, immune thrombocytopenia, thrombocytopenia, and transverse myelitis within 1-42 days in individuals vaccinated with the Ad26.COV2.S vaccine and in corresponding individuals vaccinated with the BNT162b2 vaccine, or during a control window within the same individual.
- the incidence of autoimmune thyroiditis, acute aseptic arthritis, multiple sclerosis (including optic neuritis), and Type 1 diabetes mellitus **within 1-365 days** in individuals vaccinated with the Ad26.COV2.S vaccine and in corresponding individuals vaccinated with the BNT162b2 vaccine.

Secondary Objective

• The secondary objective for this study is to describe the number of individuals who received a second dose of Ad26.COV2.S as well as their baseline demographic characteristics.

8. RESEARCH METHODS

8.1. Study Design

8.1.1. Overview of Study Design and Setting

This is a retrospective observational study using health insurance claims databases in the US. Eligible individuals will be included in the study from the time of EUA of the Ad26.COV2.S vaccine in the US, and the study will end at the last date of data availability in each database.

The study design will depend on whether the AESI is an acute or non-acute event. The primary study design for acute events (events expected to occur within 60 days of vaccination) will be a self-controlled risk interval (SCRI) design conducted in the Ad26.COV2.S exposed cohort. For non-acute events, a cohort design will be used comparing individuals exposed to Ad26.COV2.S with concurrent active comparators (individuals exposed to at least the first dose of the primary series of BNT162b2 [Pfizer-BioNTech COVID-19 vaccine]). In sensitivity analyses, a cohort design with a concurrent active comparator will be used to assess acute events.

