8.1.1.1. Self-controlled Risk Interval Design (Primary Study Design for Acute Events)

The SCRI design will compare the risk of the AESIs in a postvaccination risk window to a postvaccination control window within the same individual, in a cohort of individuals vaccinated with Ad26.COV2.S (Figure 1). The use of a postvaccination control window (rather than a prevaccination control window) avoids bias due to healthy user vaccinee effect. To account for the possibility that increased risks of AESIs might extend beyond the risk interval, the risk and control windows may be separated by buffer periods for events that do not have well established risk intervals in the literature (to be defined in the statistical analysis plan [SAP]).

[figure not shown]

Figure 1: Self-Controlled Risk Interval Design

8.1.1.2. Cohort Design With Concurrent Active Comparator (Primary Study Design for Non-acute Events and Sensitivity Analysis for Acute Events)

[figure not shown]
For the cohort design, the incidence of AESIs will be compared between the 1-dose Ad26.COV2.S exposed cohort and the 2-dose BNT162b2 comparator cohort (Figure 2):

- **Exposed cohort**: individuals will have received at least 1 dose of Ad26.COV2.S administered according to US recommendations (BLA approval or EUA). The reference date will be the first date of receipt of Ad26.COV2.S.
- Active comparator cohort: individuals will have been vaccinated with at least 1 dose of the primary series of BNT162b2 at any time on or after the start of the study observation period. The reference date of the comparator cohort will be the calendar date of the first dose in the primary series of BNT162b2. Individuals will be matched by propensity scores (PS) and calendar time (within 2 weeks) at the reference date using a 1:4 ratio of exposed to comparator within the Data Partner distributed database, if feasible; the matching ratio will be dependent on the findings of the relative uptake of vaccinations identified during feasibility assessments and monitoring.

COVID-19 vaccines were first administered to priority populations at high risk of severe disease or exposure, including older adults or those with comorbidities. Therefore, information on the presence of comorbidities within 1 year prior to the reference date and older age will be collected and included in the PS models. The covariates for the propensity score models, to be assessed up to the reference date, are described in Section 8.7.2.1.

[figure not shown]

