8.2. Setting and Study Population

8.2.1. Study Setting

This study will be conducted using health plan claims data held by 4 large national insurers that participate in the FDA's Sentinel System, including CVS Health (Aetna), HealthCore (Anthem), Humana, and Optum. Further information on the data sources used in this study can be found in Section 8.4. The study period will begin on 27 February 2021, the day Ad26.COV2.S was authorized for emergency use in the US, although data from before 27 February 2021 will be used to define patient characteristics and vaccine history.

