8.9. Limitations of the Research Methods

Given the broad list of potential events that could be associated with the Ad26.COV2.S vaccine and the large heterogeneity in the type of events, acute versus long latency diseases, different study design approaches will be used depending on the type of event. For acute events, the primary study design will be the SCRI design (Baker 2015), which is preferred due to its inherent control for time-constant factors; additionally, because it is restricted to vaccinated individuals, it avoids bias due to misclassification of unexposed individuals due to vaccination outside traditional medical care settings, which may not be captured in health plan data. For non-acute events, the primary study design will be the cohort design with active comparators, which avoids bias due to temporal trends in healthcare utilization for events of interest over time, differential outcome misclassification by exposure group (relieving concern of missing vaccine doses as everyone has recorded vaccine information), and confounding by vaccine hesitancy, healthcare access, or personal health beliefs and behaviors. (Lund 2015)

Experience with other vaccines indicates that safety risks may occur within specific periods postvaccination, for example, the risk of Guillain-Barré syndrome within 6 to 8 weeks after the

swine flu vaccine. However, for most of the AESIs included in this study, the risk windows are not clearly established; theoretical risk periods based on previous experience, mechanistic evidence and biological plausibility are considered. For this reason, a subset of the listed AESIs (to be defined in the SAP) will also be assessed within a larger risk period in sensitivity analyses.

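### Entry to the BNT162b2 comparison has no end date, so it takes in vaccinees after the 5 May 2022 EUA restriction, for whom Section 8.9's argument for the active comparator does not hold

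*Protocol*

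**What the plan says.** Entry window. Section 8.2.1 states: "The study period will begin on 27 February 2021, the day Ad26.COV2.S was authorized for emergency use in the US". Section 8.1.1 gives the other end: "the study will end at the last date of data availability in each database". The inclusion and exclusion criteria under Section 8.2.2.2 set enrolment, age and prior-vaccination conditions, but no last entry date. Footnote b to the Section 5 milestones expects that "data extraction (querying) Q2-Q3 2023 will include data through ~ Q2-Q3 2022".

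Restriction. Section 6.2 reports: "On 05 May 2022, the FDA further revised the EUA, limiting use of the Ad26.COV2.S vaccine". Two groups remained: adults "for whom other authorized or approved COVID-19 vaccines are not accessible or clinically appropriate", and adults who choose it "because they would otherwise not receive a COVID-19 vaccine".

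Exposed cohort. Section 8.1.1.2 ties membership to the authorization in force: "individuals will have received at least 1 dose of Ad26.COV2.S administered according to US recommendations (BLA approval or EUA". Each exposed person is matched, 1:4 if feasible, on propensity score and on calendar time within 2 weeks.

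Justification. Section 8.9 says the active comparator avoids, among other things, "confounding by vaccine hesitancy, healthcare access, or personal health beliefs and behaviors". The same section later says that beliefs, educational level and socioeconomic status cannot be considered because they are unrecorded or incompletely recorded, and that residual bias may remain in the cohort designs.

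**The concern.** The argument for an active comparator is that people who receive either vaccine are alike in willingness to be vaccinated, access to care and health beliefs. From 5 May 2022 the authorization made those characteristics the route into the Ad26.COV2.S group. Matching within 2 weeks then pairs a late Ad26.COV2.S recipient with someone who obtained and accepted BNT162b2 in the same weeks. That is the contrast the design was meant to avoid.

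The current version is dated 20 October 2022 and describes the restriction in Section 6.2. No eligibility rule, propensity score covariate, stratum or sensitivity analysis in it responds to the restriction.

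At stake are the primary analysis of autoimmune thyroiditis, acute aseptic arthritis, multiple sclerosis and Type 1 diabetes, and the cohort sensitivity analysis of the acute AESIs. The SCRI compares each vaccinee with himself or herself and is not touched.

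**Working it through.** **1. Length of the overlap.** Start 27 February 2021 (Section 8.2.1); restriction 5 May 2022 (Section 6.2). The last data date is taken as a quarter end, because footnote b gives only quarters.

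- To 30 June 2022: 489 days, 56 of them after 5 May (56/489 = 11.5%).
- To 30 September 2022: 581 days, 148 of them after 5 May (148/581 = 25.5%).

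The overlap is therefore about 2 to 5 months. A database whose data stopped early in Q2 2022 would have none. These are shares of calendar time, not of vaccinees; the protocol gives no share of vaccinees.

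**2. What the propensity score covers.** Section 8.3.2 lists comorbidities, immunocompromised states, utilization, geography, a socioeconomic proxy if feasible, and indicators of each prior AESI. Clinical unsuitability of another vaccine is partly measured through these. Refusal and beliefs are not measured. Access is covered only indirectly, by utilization, geography and the enrolment requirement.

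**3. Possible effect on the pooled rate ratio.** Let f be the share of exposed person-time from post-restriction entrants, and k their baseline AESI rate relative to their matched comparators. Then

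IRR observed / IRR true = (1 − f) + f·k.

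Both inputs are assumptions:

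| f | k = 0.5 | k = 2 | k = 3 |
|---|---|---|---|
| 0.5% | 0.9975 | 1.005 | 1.01 |
| 1% | 0.995 | 1.01 | 1.02 |
| 2% | 0.99 | 1.02 | 1.04 |

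**4. Is that range of f plausible for the 1-365 day outcomes?** Late entrants have at most 56 to 148 days of follow-up, with a mean L of about 28 to 74 days if entry is even. Suppose earlier entrants average E = 200 to 365 days (assumption). The share of persons needed to give person-time share f is p = fE / [fE + (1 − f)L].

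- f = 0.5%, E = 200, L = 74: 1 / (1 + 73.63) = 1.3%.
- f = 2%, E = 365, L = 28: 7.3 / (7.3 + 27.44) = 21%.

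The rationale for Amendment 2 expects minimal additional uptake, so the upper part of the range is unlikely. For the acute outcomes, with windows of at most 42 days after a dose, truncation removes less, and the share of person-time is closer to the share of persons.

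**5. Comparison with sampling error.** Take 100,000 exposed and 400,000 comparators (Section 8.5.2), followed for a full year with no effect.

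- At 50 per 100,000 person-years: 50 and 200 events; exp(1.96 × √(1/50 + 1/200)) = 1.36.
- At 382, the highest non-acute rate in Table 1 (Type 1 diabetes): 382 and 1,528 events; exp(1.96 × √(1/382 + 1/1,528)) = 1.12.

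The confidence limits are thus about 12% to 36% above the estimate, against an illustrative bias between −1% and +4%.

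**6. Precision cost of a cut-off.** The Section 8.5.2 example first: 100,000 exposed, 1:4, 60 days, 50 per 100,000 person-years, RR 1.0. Expected events are a = 100,000 × (60/365.25) × 0.0005 = 8.21 and b = 4a = 32.85. The probability that the upper limit is below 3.0 is Φ[ln 3 / √(1/a + 1/b) − 1.96] = 0.804, against 0.805 in the protocol. At RR 1.2, with a = 9.86 and ln(3/1.2), it is 0.713, against 0.714. Both reproduce. Removing part of the exposed group and its matches gives:

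| Exposed removed (assumed) | RR 1.0 | RR 1.2 |
|---|---|---|
| none | 0.804 | 0.713 |
| 1% | 0.800 | 0.709 |
| 5% | 0.784 | 0.691 |
| 10% | 0.762 | 0.668 |

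**The case against.** The strongest reply is that this changes no conclusion: late uptake is expected to be minimal, late follow-up is short, and a shift of a few percent sits well inside the confidence interval. Section 8.9 also concedes residual bias from unmeasured confounders, and keeping every first-dose vaccinee matches the stated objective. The point about size stands. The concession in 8.9 is general, though. It does not mention the restriction, and it leaves the claim about hesitancy, access and beliefs unqualified.

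A reader might go further and infer that late vaccinees have no exchangeable comparator at all. The documents do not support that. People in the second EUA group choose Ad26.COV2.S and may have had BNT162b2 available and declined it. All entrants have at least a year of medical and drug coverage, which narrows the access group. Comparators matched within 2 weeks also have their first observed dose in mid-2022 and are late adopters too. Actual use may have departed from the authorization.

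A reader might also infer a clear upward bias. Nothing in the protocol gives the relative rate in late vaccinees; a value below 1 biases the ratio downward.

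Anaphylaxis looks like the natural example, since it can rule out another vaccine. Its primary analysis is the SCRI, however. In the cohort sensitivity analysis it has a 180-day washout and a prior-event indicator in the propensity score.

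**Conclusion.** The point holds as a foreseeable and avoidable weakness for a small group of entrants, not as a flaw that invalidates the primary non-acute analysis. The protocol's text establishes that entry has no end date, that data are expected to run past 5 May 2022, and that the authorization then selected on the factors Section 8.9 says the comparator removes. It does not establish how many people are involved or which way their rates differ. On the assumed inputs the pooled rate ratio changes by a factor of about 0.99 to 1.04. The case for acting is that the remedy costs very little.

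**What to change.** In Section 8.2.2.2, end entry to both active-comparator cohorts on 4 May 2022; people already entered keep their planned follow-up. At minimum, pre-specify a sensitivity analysis of the cohort comparison with that cut-off.

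Keep later vaccinees in the SCRI and in the second-dose description. Section 8.7.6 draws that description from the exposed cohort, so it would need to say that the cut-off does not apply there.

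In Section 8.9, limit the claim about hesitancy, access and beliefs to entry before the restriction, and reconcile it with the later statement that beliefs cannot be considered.

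The cost is one date in the eligibility rule and the loss of a few vaccinees with short follow-up. If 1% of the exposed are lost, the Section 8.5.2 example falls from 0.804 to 0.800. The cohort comparison would also no longer describe use under the restricted EUA, and the report should say so.
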